#### **Outcome Definitions**

The degree of blood contamination of the specimen was based on the pathologist evaluation of the formalin fixed and paraffin embedded (FFPE) tissue samples and defined as significant when a large amount of blood cells made pathological diagnosis difficult to be made. On the other hand, blood contamination of the specimen was defined as not significant when no or only few blood cells were present without any influence on the pathological diagnosis.

Sensitivity was defined as the true positive rate whereby the test was the final cytologic diagnosis, Specificity as the true negative rate (proportion of actual negatives that are correctly identified as such), PPV was defined as the number of true positive divided the number of positive calls (true positive and false positive), NPV was defined as the number of true negative divided the number of negative calls (true negative and false negative). Diagnostic accuracy was defined as the ratio between the sum of true positive and true negative values divided by the total number of masses.

Technical success was defined as the capability of sampling the target lesion associated with the presence of a visible core, according to endosonographer's judgment, potentially useful for the final pathological analysis.

Adverse events were defined based on the criteria expressed by Cotton et al. [Cotton PB. Gastrointest Endosc 2010;71:446-54]

Samples positive for malignancy were considered diagnostic for malignancy, while in patients with negative EUS-FNB, surgical specimen evaluation, results of other diagnostic investigations and/or a clinical follow-up of at least 6 months were used to establish the definitive diagnosis.

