#### RESULTS

From May 2017 to May 2018, a total of 182 consecutive patients were screened for participation in this study, of whom 72 were excluded, while 110 patients constituted the study cohort and were randomized to one of two groups: stylet slow-pull technique (55 patients) and standard suction technique (55 patients) as showed in figure 1. Overall, there were 49 male (44.5%) and 61 female (55.5%), with a mean age of 70.9±11.3 years. Patients' and lesions' characteristics are shown in Table 1 and appeared similar in both groups. The majority of lesions were located in the head of the pancreas (72 lesions corresponding to 65.5%) with similar rates in slow-pull group (69%) and in the standard suction group (62%). No difference in mean size of the lesions was found between the two groups(35.9±19.9 vs 37.6±14.1 cm; p=ns).

Technical success was achieved in 95% of patients (slow pull technique 96% vs standard suction technique 94%, p=ns) with a not-significant blood contamination of the specimen in 85 patients (overall 77.3%: slow-pull 80% vs standard suction 74%, p=ns). A diagnosis of malignancy was obtained in 98 cases as showed in Table 2. Fifty were in the slow-pull group and 48 in the standard suction group. In 6 patients (1 in the slow-pull and 5 in the standard suction group) with a benign histological diagnosis at EUS-FNB the definitive diagnosis was chronic pancreatitis. Thus, these patients were considered true negative. Finally there were 6 false negative cases (4 in the slow pull technique group and 2 in standard suction group). Comparing the two groups (Table 3), the sensitivity, specificity, negative likelihood ratio, positive likelihood ratio, and diagnostic accuracy were 96 vs 93%, 100% vs 100%, 0.04 vs 0.07, "infinity" in both, and 96 vs 93%, respectively without any statistical difference between them. No procedure-related adverse events were observed in the two groups.

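### The reference standard lets a negative biopsy be settled as benign on another investigation alone, without surgery or the 6-month follow-up, so a missed cancer could count as a true negative

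*Combined protocol and SAP*

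**What the plan says.** The Outcome Definitions section treats the two biopsy results differently.

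- **Positive biopsy:** "Samples positive for malignancy were considered diagnostic for malignancy". No further confirmation is required.
- **Negative biopsy:** the definitive diagnosis rests on other sources, namely "in patients with negative EUS-FNB, surgical specimen evaluation, results of other diagnostic investigations and/or a clinical follow-up of at least 6 months".

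The document does not say which other investigations count, whether a non-malignant result from one of them can close a case by itself, or who decides. Materials and methods blinds the pathologists to group. No blinding is stated for whoever assigns the definitive diagnosis.

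RESULTS then reads "In 6 patients (1 in the slow-pull and 5 in the standard suction group) with a benign histological diagnosis at EUS-FNB" and gives the definitive diagnosis of these six as chronic pancreatitis. They are counted as true negatives. The route by which each was verified is not reported.

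Sensitivity, specificity, PPV, NPV and diagnostic accuracy are secondary outcomes under Outcome measures. The primary endpoint is blood contamination of the specimen.

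**The concern.** Joining the routes with *and/or* makes each sufficient alone, so the 6-month minimum applies only where follow-up is the route used. The routes are not equally able to support a benign label. Another investigation can establish malignancy. A non-malignant result soon after the biopsy does not exclude a cancer that both tests missed, and excluding it is what the follow-up is for.

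The error would run in one direction: a missed cancer labelled benign moves from false negative to true negative and raises sensitivity, NPV and accuracy. Specificity would not reveal it. Positive samples are accepted as malignant, so no false positive can arise and specificity is 100% by rule while any true negative remains.

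The trial's own figures show that the risk is not remote. Of the 12 negative biopsies, 6 were false negatives. The benign labels are also split 1 against 5, so errors among them need not cancel between arms.

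**Working it through.** **Inputs (all from RESULTS)**

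- Randomised: "stylet slow-pull technique (55 patients) and standard suction technique (55 patients").
- True positives (TP): "A diagnosis of malignancy was obtained in 98 cases"; "Fifty were in the slow-pull group and 48 in the standard suction group".
- True negatives (TN): 1 slow-pull, 5 suction.
- False negatives (FN): "6 false negative cases (4 in the slow pull technique group and 2 in standard suction group").

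I take the 98 malignant diagnoses as biopsy true positives. This is supported by 98 + 6 + 6 = 110, and by arm by 50 + 4 + 1 = 55 and 48 + 2 + 5 = 55.

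**Step 1. The printed figures.** RESULTS states that sensitivity, specificity, negative and positive likelihood ratios and accuracy "were 96 vs 93%, 100% vs 100%, 0.04 vs 0.07, 'infinity' in both, and 96 vs 93%, respectively". From the counts:

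| | Formula | Slow-pull | Suction |
|---|---|---|---|
| Sensitivity | TP/(TP+FN) | 50/54 = 92.6% | 48/50 = 96.0% |
| Negative likelihood ratio (specificity 100%) | 1 − sensitivity | 0.07 | 0.04 |
| Accuracy | (TP+TN)/N | 51/55 = 92.7% | 53/55 = 96.4% |
| NPV | TN/(TN+FN) | 1/5 = 20% | 5/7 = 71.4% |

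In the slow-pull, suction order that the section uses, the printed values are not reproduced. They match with the arms transposed.

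**Step 2. Does the transposition matter here?** Either the percentages are transposed, or the arm labels of all the counts are. Relabelling only some of the counts breaks the total of 55 per arm. For example, exchanging only the false negatives gives 50 + 2 + 1 = 53 and 48 + 4 + 5 = 57; exchanging both TP and FN gives 48 + 2 + 1 = 51 and 50 + 4 + 5 = 59. Under both readings that keep 55 per arm, the arm with five benign labels is the arm at 96%. The fragility below is therefore the same size either way, and only the arm's name is in doubt. I use the labels attached to the counts.

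**Step 3. Recode benign labels as false negatives.** With j wrong calls in slow-pull (0 or 1) and k in suction (0 to 5), sensitivity is 50/(54 + j) and 48/(50 + k).

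| j | k | Slow-pull | Suction | Order reversed? | Fisher p |
|---|---|---|---|---|---|
| 0 | 0 | 92.6% | 96.0% | – | 0.68 |
| 0 | 1 | 92.6% | 94.1% | no | 1.0 |
| 0 | 2 | 92.6% | 92.3% | yes, by 0.3 points | 1.0 |
| 0 | 5 | 92.6% | 87.3% | yes | 0.53 |
| 1 | 0 | 90.9% | 96.0% | no | 0.44 |
| 1 | 1 | 90.9% | 94.1% | no | 0.72 |
| 1 | 5 | 90.9% | 87.3% | yes | 0.76 |

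Over all 12 combinations of j and k, the Fisher p-value for sensitivity lies between 0.44 and 1.0.

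Six patients give 15 possible pairs. Ten pairs lie wholly in suction and reverse the order; the other five take one patient from each arm and do not.

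**Step 4. Other measures.** With j = 0 and k = 2, accuracy ties at 51/55 (92.7%) and suction NPV falls from 5/7 (71.4%) to 3/7 (42.9%). Accuracy is not significant in any of the 12 combinations (p from 0.44 to 1.0). NPV rests on 5 and 7 patients and is very unstable: the single combination j = 1, k = 0 gives 0/5 vs 5/7, with Fisher p = (21 + 1)/792 = 0.028. The other 11 give p above 0.05.

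**The case against.** The strongest case on the other side has four parts.

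1. **No misclassification is shown.** The six patients had a benign histological result and a specific definitive diagnosis, chronic pancreatitis; they were not merely left as not malignant. No text says that a case was closed early or without follow-up. The reference standard also did its work on the other six negative biopsies, finding cancer in both arms. All of this stands. A reader might infer that the accuracy results are biased; the documents support only that the rule permits such bias and that a reader cannot exclude it.
2. **The reversal is conditional and small.** A reader might infer that any two wrong calls would reverse the arms. Both must fall in suction, the gap is then 0.3 points, and the statement of no statistical difference in sensitivity and accuracy survives every combination. The 1 against 5 split is itself compatible with chance (1/55 vs 5/55, Fisher p = 0.21). This stands.
3. **The printed percentages put slow-pull ahead,** so recoding suction patients would widen the gap. That needs both the percentages and the true-negative labels to be right, which 55 patients per arm does not allow with these counts. The conflict is nevertheless the firmer defect and comes first.
4. **Changing the rule after results by arm are known is heavy,** and recoding can penalise suction five times and slow-pull once. This stands as a reason to present the recoding as a bound and to label it post hoc. It is no reason to leave the verification routes unreported.

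**Conclusion.** The point holds as an avoidable risk of bias in the secondary accuracy outcomes. It is not a demonstrated error. The wording allows a benign label without surgery or the 6-month follow-up, and the documents do not report which route settled each of the six benign cases.

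Its size, on the labelled counts: two wrong calls in suction could take sensitivity from 96.0% to 92.3%, against 92.6% for slow-pull, and NPV from 71.4% to 42.9%. One wrong suction call, or one in each arm, leaves the order unchanged. No combination makes sensitivity or accuracy differ significantly, and the blood-contamination endpoint is unaffected.

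This assumes that the 98 malignant diagnoses are biopsy true positives and that the counts are right apart from a possible exchange of arm labels. The number of wrong calls is hypothetical; the documents are compatible with none. If all six had surgery or completed follow-up, one sentence saying so would settle the matter.

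**What to change.** 1. Reconcile the printed sensitivity, negative likelihood ratio and accuracy with the patient counts, and correct whichever is transposed.
2. Reword the definition, for the accuracy analysis only, along these lines: other investigations may establish malignancy; a benign definitive diagnosis requires a surgical specimen or at least 6 months of clinical follow-up without malignancy.
3. Take the status of all 12 biopsy-negative patients at one common cut-off, 6 months after the last enrolment. With entry from May 2017 to May 2018, this gives about 6 to 18 months of potential follow-up.
4. Report by arm the route that settled each biopsy-negative case.
5. Add a sensitivity analysis that recodes benign cases lacking surgery or completed follow-up as false negatives. Present it as a worst-case bound and, since results by arm are known, as post hoc.

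The cost is one sentence in the definition, one extra analysis and a status check on 12 patients. The check assumes that their records can be consulted, which the documents do not describe. Patients lost before 6 months stay unverified, and the estimates may look slightly less favourable.

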# **Statistical Analysis**

The sample size was calculated based on the results of a previous study [Nakai Y. Dig Dis Sci. 2014;59:1578-85] that showed that blood contamination of the specimen was lower with the stylet slow-pull technique as compared with the standard suction technique (25% vs 70%), with a consequent increase in the diagnostic accuracy. Based on these data we calculated for a difference of 25%, at a power of 80% and an alpha of 0.05 (two-sided test), a final sample size of 110 patients (55 patients in each group). Continuous variables will be reported as mean ± standard deviation (SD). Categorical variables will be presented as numbers and percentage and will be compared either using the chi-square test (with Yates' correction when appropriate) or Fisher exact test.

Statistical was conducted using the Fisher's exact test for categorical variables and the Mann–Whitney U-test for continuous variables. Sensitivity, specificity, positive predictive value (PPV), negative predictive value (NPV), and overall diagnostic accuracy for each arm were investigated by comparing the results with the definitive diagnosis. Statistical tests were considered

significant at a corresponding p value of <0.05. Data handling and analyses were done with SPSS 14.

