#### **Outcome measures**

The primary end point of the study was the degree of blood contamination of the collected specimens in patients with pancreatic solid lesions who underwent EUS-FNB using the 20Gauge Procore Needle and the slow pulling or the standard aspiration techniques. Secondary outcomes were technical success, comparison of the performance of the two techniques during EUS-FNB in terms of sensitivity, specificity, positive predictive value (PPV), negative predictive value (NPV), and diagnostic accuracy, and occurrence of adverse events.

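### The stated 80% power for a 25-point difference lacks its two rates, and under Fisher's exact test 55 per arm gives about 72% (25% vs 50%) or 69% (45% vs 70%)

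*Combined protocol and SAP*

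**What the plan says.** Under Outcome measures, the primary endpoint is the degree of blood contamination. Outcome Definitions makes it binary: significant or not significant.

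The Statistical Analysis section starts from an earlier study in which contamination was "lower with the stylet slow-pull technique as compared with the standard suction technique (25% vs 70"%), a gap of 45 points. It then says "we calculated for a difference of 25%, at a power of 80% and an alpha of 0.05 (two-sided test"), and arrives at 110 patients, 55 per group. It does not give the pair of rates, the formula or the test used for sizing.

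Two sentences in the same section deal with the test. One says that categorical variables "will be compared either using the chi-square test", with Yates' correction where appropriate, or by Fisher's test. The next paragraph reads "Statistical was conducted using the Fisher's exact test for categorical variables".

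The RESULTS section gives the primary result as non-significant "blood contamination of the specimen in 85 patients (overall 77.3%: slow-pull 80% vs standard suction 74%, p=ns"). No interval is given.

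**The concern.** The power to detect a difference between two proportions depends on the rates as well as on the gap. A 25-point gap near 50% is harder to detect than one near 0% or 100%. With only the gap stated, the 80% is a claim the reader cannot check, and the one pair that is printed (25% vs 70%) is not a 25-point pair.

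The test matters too. Fisher's test is conservative at this sample size, so a number obtained from an uncorrected normal approximation does not deliver its nominal power when the data are analysed by Fisher. If that happened here, the stated power is too high for the test said to have been used. Because the primary result is null and reported only as non-significant, the stated power is all the reader has for judging how informative that result is.

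**Working it through.** **Inputs.** From Statistical Analysis: difference 25 points, power 80% (z = 0.8416), two-sided alpha 0.05 (z = 1.9600), 55 per arm, cited rates 25% and 70%, Fisher's test. The 25-point pair is not given, so it is an assumption. The two natural choices keep one cited rate in its own arm: 25% vs 50%, or 45% vs 70%.

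**Step 1: reproduce 55 per arm.** The unpooled normal formula without continuity correction is

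n = (z_a + z_b)² × [p1(1−p1) + p2(1−p2)] / d², with (1.9600 + 0.8416)² = 7.849.

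- 25% vs 50%: 7.849 × (0.1875 + 0.2500) / 0.0625 = 54.94, so 55.
- 45% vs 70%: 7.849 × (0.2475 + 0.2100) / 0.0625 = 57.45, so 58.
- 25% vs 70%, as cited: 7.849 × (0.1875 + 0.2100) / 0.2025 = 15.4, so 16.

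The other common two-sided formulas give, per arm:

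| Pair | Unpooled | Pooled | Continuity-corrected |
|---|---|---|---|
| 25% vs 50% | 54.94 | 57.67 | 65.43 |
| 45% vs 70% | 57.45 | 60.19 | 67.95 |
| 25% vs 70% | 15.4 | 18.1 | 22.3 |

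The most plausible source of 55 is 25% vs 50% by the unpooled formula, but it is not the only one. Unpooled 24% vs 49% (54.29), pooled 21% vs 46% (54.76) and continuity-corrected 13% vs 38% (54.22) also round up to 55. Keeping the cited 70% gives 58, 61 or 68, never 55.

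**Step 2: exact power at 55 per arm.** List all 56 × 56 possible tables, mark those with two-sided p < 0.05, and add up their binomial probabilities. At this size, Fisher and Yates reject exactly the same tables.

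| Pair | Fisher = Yates | Uncorrected chi-square |
|---|---|---|
| 25% vs 50% | 72.1% | 78.9% |
| 45% vs 70% | 68.8% | 75.8% |
| 24% vs 49% | 72.8% | 79.5% |
| 21% vs 46% | 75.0% | 81.2% |
| 13% vs 38% | 82.0% | 87.2% |

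Against the stated 80%, the shortfall under Fisher is 80 − 72.1 = 7.9 points or 80 − 68.8 = 11.2 points for the two pairs built on a cited rate. Of the pairs listed, only 13% vs 38% holds 80% under Fisher, and it contains neither cited rate.

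**Step 3: what would give 80% under Fisher.**
- With 55 per arm and a 25-point gap: a lower rate of about 14.8% or less or, by symmetry, a higher rate of about 85.2% or more.
- With 55 per arm and one cited rate fixed: a gap of 27.5 points up from 25%, or 28.3 points down from 70%.
- With a 25-point gap at the anchored pairs: 64 per arm for 25% vs 50% (63 gives 79.4%, 64 gives 80.2%) and 69 per arm for 45% vs 70% (68 gives 79.7%, 69 gives 80.4%).

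**Step 4: the reported result.** 80% of 55 is 44, and 85 − 44 = 41, so non-significant contamination was 44/55 (80.0%) vs 41/55 (74.5%; the text prints 74%). The p-values are 0.65 by Fisher, 0.65 by Yates and 0.49 by uncorrected chi-square.

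The Wilson limits are 67.6% to 88.4% and 61.7% to 84.2%. Newcombe's interval for the difference of 0.0545 is then:
- lower: 0.0545 − √[(0.800 − 0.676)² + (0.842 − 0.745)²] = −0.102
- upper: 0.0545 + √[(0.884 − 0.800)² + (0.745 − 0.617)²] = +0.208

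That is +5.5 points, 95% CI −10.2 to +20.8, which excludes 25 points in either direction.

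**Step 5: power at the rates that occurred.** Pooled significant contamination was (110 − 85)/110 = 22.7%. A 25-point gap centred there is 10.2% vs 35.2%, for which Fisher power is 85%.

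**The case against.** The strongest reply is that 55 is not a miscalculation. The unpooled formula at 25% vs 50% gives 54.94, and with the uncorrected chi-square, which the section also lists, the exact power at that pair is 78.9%, about one point short. That stands: the gap comes from sizing with one method and analysing with another, not from a slip in the sum. It does not rescue the stated figure, because the test said to have been used is Fisher's, and at both anchored pairs even the uncorrected chi-square is below 80%.

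Second, the 72% and 69% rest on assumed rates, and 13% vs 38% or its mirror 62% vs 87% would give 82.0% under Fisher. This also stands, so the shortfall is conditional. The omission of the rates is not.

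Third, planning for 25 points after citing 45 is cautious: at the cited 25% vs 70%, Fisher power with 55 per arm is 99.7%. That is fair, but the claim made is 80% for 25 points.

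Fourth, recruitment is complete and the conclusion is unaffected, so restated power may seem academic. The correction is cheap, though, and the interval is what a reader of a null result needs.

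Two caveats on the interval are accepted. Technical success of 96% and 94% implies about 53 and 52 patients with a visible core. If the others had no gradable specimen, 44/53 vs 41/52 gives +4.2 points (−11.0 to +19.2). The printed 85 = 77.3% does, however, imply a denominator of 110. And the interval excludes 25 points but still allows about 21 in favour of slow-pull, so it does not show equivalence.

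**Conclusion.** The concern holds. The 80% power cannot be verified, because the two rates and the formula are missing and the analysis test is described in two ways. If either cited rate anchors the 25-point pair, power under Fisher's test with 55 per arm is 72.1% or 68.8%, about 8 to 11 points below the stated figure. The size of the shortfall depends on those assumed pairs. It disappears only for pairs near the extremes, which contain neither cited rate.

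The shortfall belongs to the planning rates: at the observed pooled rate, Fisher power for 25 points is 85%. The primary result is non-significant under every listed test. This should be fixed as a matter of reporting and does not threaten the conclusion.

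**What to change.** 1. State the two assumed rates and the formula behind 55 per arm. Then either restate the power under Fisher for those rates (about 72% for 25% vs 50%, about 69% for 45% vs 70%) or give the difference detectable with 80% power, about 28 points.
2. Name Fisher's exact test as the single test for the primary endpoint, and remove the sentence offering chi-square, Yates or Fisher, or qualify it so that it no longer competes. Do not move to the uncorrected chi-square now that the results are known.
3. Report the primary difference with its interval beside the 25-point design difference: non-significant contamination 44/55 vs 41/55, +5.5 points, 95% CI −10.2 to +20.8 (Newcombe). Say how patients without a visible core were graded.

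The cost is wording in one section and one added result. The stated power becomes less favourable. No extra patients are needed and the reported conclusion does not change.

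### The Statistical Analysis section does not fix one test for the binary primary outcome, and the test it names second, Fisher's, is valid but conservative at 55 per arm

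*Combined protocol and SAP*

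**What the plan says.** The outcome concerned is defined in two places. Under Outcome measures, "The primary end point of the study was the degree of blood contamination of the collected specimens". Under Outcome Definitions, contamination is "defined as significant when a large amount of blood cells made pathological diagnosis difficult to be made", and is otherwise not significant. The primary comparison is therefore a 2x2 table.

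The Statistical Analysis section then speaks twice about categorical variables:

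- First, they are to be compared by "chi-square test (with Yates' correction when appropriate) or Fisher exact test". No criterion is given for choosing between the tests or for applying the correction.
- In the next paragraph, "Statistical was conducted using the Fisher's exact test for categorical variables and the Mann–Whitney U-test for continuous variables".

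Neither sentence sets the primary outcome apart. The sample-size text gives a 25-point difference, 80% power, two-sided alpha 0.05 and 55 patients per group. It names neither the test assumed nor the two rates that are 25 points apart. The only rates printed there are the 25% vs 70% of an earlier study. The Results section reports the primary comparison as not significant, with no p value and no test named.

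**The concern.** Three tests are open for the primary outcome under the first sentence and one under the second. Where they can reach different verdicts on the same table, an unfixed choice lets the conclusion depend on a decision made after the data are seen. Reporting only that the result was not significant leaves a reader unable to tell which test was used.

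There is also a cost in following the second sentence to the letter. Fisher's test conditions on both margins, and in a well-filled table of this size its real error rate falls well below the nominal 5%. That unused error rate is lost power, in a trial sized for 80%.

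**Working it through.** **Inputs.** 55 per arm, two-sided p < 0.05 and a 25-point difference, all from Statistical Analysis. The pair of rates is not stated, so several pairs 25 points apart are used as assumptions, with 25% vs 50% as the main case. The cited 25% vs 70% is shown alongside.

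**The plan's own figure.** The unpooled normal formula at 25% vs 50% gives

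n = (1.960 + 0.842)² × (0.25×0.75 + 0.50×0.50) / 0.25² = 7.849 × 0.4375 / 0.0625 = 54.9, so 55 per arm.

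At the same rates the pooled formula gives 58 and the continuity-corrected formula 66. The stated size thus fits an uncorrected two-sided calculation. This does not prove what was done: a one-sided continuity-corrected formula at 45% vs 70% also returns 55, although the text says two-sided.

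**Enumeration.** Each arm can have 0 to 55 contaminated specimens, so there are 56 × 56 = 3,136 tables. For each, the Fisher, Pearson and Yates p values were computed. Boschloo's test uses Fisher's p value as its statistic; its rejection region here is Fisher p ≤ 0.0732. Power, size and probability of disagreement are sums of the products of binomial probabilities over the relevant tables.

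- Fisher and uncorrected chi-square disagree on 106 tables. In all of them chi-square rejects and Fisher does not.
- Fisher and Yates disagree on none.

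| Rates | Fisher or Yates power | Boschloo power | Uncorrected chi-square power | Fisher and chi-square disagree |
|---|---|---|---|---|
| 25% vs 50% | 72.1% | 77.0% | 78.9% | 6.8% |
| 45% vs 70% | 68.8% | 74.7% | 75.8% | 7.0% |
| 20% vs 45% | – | – | – | 6.1% |
| 25% vs 70% (cited) | 99.7% | – | 99.8% | 0.14% |

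Maximum actual size over all common rates: Fisher and Yates 3.2%, Boschloo 4.7%, uncorrected chi-square 5.3%. Boschloo's gain over Fisher is 77.0 − 72.1 = 4.9 points in the first row and 74.7 − 68.8 = 5.9 in the second.

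**A table where the choice decides.** For 11/55 vs 21/55 (hypothetical), the cross-product difference is 11×34 − 21×44 = −550, so

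χ² = 110 × 550² / (55 × 55 × 32 × 78) = 4.41, p = 0.036.

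Fisher gives p = 0.058. That is below 0.0732, so Boschloo also rejects.

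**The reported result.** The Results section gives 85 of 110 without significant contamination, 80% vs 74%. This is consistent with 44/55 and 41/55, so 11/55 vs 14/55 contaminated. The cross-product difference is 11×41 − 14×44 = −165, and

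χ² = 110 × 165² / (55 × 55 × 25 × 85) = 0.47, p = 0.49.

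Yates and Fisher both give p = 0.65. Boschloo does not reject either, since 0.65 is far above 0.0732.

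**Sparse secondary outcomes.** Technical success of 96% and 94% is consistent with 53/55 and 52/55: 5 failures, or 2.5 expected per arm. The 6 false negatives give 3 expected per arm for accuracy. For sensitivity, with 50 + 4 = 54 and 48 + 2 = 50 malignant cases, the expected counts are 6 × 54/104 = 3.1 and 6 × 50/104 = 2.9. Chi-square is unsuitable with such small counts, and Fisher is suitable.

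**The case against.** The strongest reply is that this is loose wording and no contradiction. The first sentence lists Fisher and the second names it, so an analyst who uses Fisher obeys both. The change of tense fits a menu followed by the option taken. That stands. A reader might infer that the two sentences are mutually exclusive, or that they disagree in 7% of trials whichever way the first is read. The documents support neither: the figure applies only to the uncorrected chi-square, and it is zero for Yates or Fisher.

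The figure also rests on assumed rates, and at the only printed pair it is negligible. That stands as well, although 25 points is the plan's own design difference.

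A reader might further infer that Fisher makes the analysis invalid, or that its conservatism buys nothing. Neither holds. Fisher keeps the error rate below 5%, whereas the uncorrected chi-square can reach 5.3%, so part of the 7-point power gap to chi-square is paid for in size. Only the comparison with Boschloo, about 5 to 6 points, is a gain at a controlled error rate.

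Finally, results already exist and are insensitive to the choice, so a newly named test cannot protect this trial's primary comparison. That is correct and limits what the fix can claim. It does not remove the need to say which test was used.

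**Conclusion.** The plan leaves the primary test open. At 55 per arm the opening matters only between the uncorrected chi-square on one side and Fisher or Yates on the other. At an assumed 25-point difference it would decide about 6 to 7% of trials, always with chi-square rejecting and Fisher not. At 25% vs 70% it would decide 0.14%.

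Following the Fisher sentence is valid, but it costs about 5 to 6 points of power against an exact test of size 4.7%. These sizes rest on the assumed pairs of rates and on all 55 patients per arm being analysed.

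The reported primary conclusion is unaffected (p = 0.49 to 0.65, taking 11/55 vs 14/55). The point is a modest one about specification and efficiency. It gives no ground for doubting the reported result or for supposing that the test was chosen to suit the data.

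**What to change.** Replace both sentences with one rule:

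- **Primary outcome:** Boschloo's unconditional exact test, two-sided 0.05. It rejects whenever Fisher does and keeps the error rate at or below 5%. If the software lacks it, use Pearson chi-square without Yates' correction.
- **Sparse secondary outcomes** (technical success, sensitivity, accuracy): Fisher's exact test.
- Delete the open-ended qualifier on Yates' correction.

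In the Results section, state which test produced the reported non-significant primary comparison and give its p value. Label any re-run with a newly named test as post hoc.

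The cost is a short rewording and one re-run on existing data. There are two downsides: Boschloo's test may need software other than the SPSS 14 named in the plan, and the fallback chi-square can slightly exceed 5% (up to 5.3%).
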